Adapted from Clinical Therapeutics, Vol. 23, Claxton AJ, Cramer J, Pierce C. A systematic review of the associations between dose regimens and medication compliance, pgs. 1296-1310, Copyright 2001, with permission from Excerpta Medica, Inc.⁴⁴

3. Study design
 1. Single-center, open-label, randomized comparative pilot trial.
 2. There will be 20 subjects in each arm, with a total study size of 40 subjects.
2. Allocation: Four random permuted-blocks of ten with equal arm allocation ratio will be used. Since no other stratification criteria are considered, larger block sizes will be appropriate. In each block, ten random numbers will be generated using SAS 9.4 with a range from zero to ninety nine. Even numbers will be assigned the intervention arm and odd numbers will be assigned the standard of care with resulting 1:1 allocation.
3. Intervention Model: Parallel assignment
4. Masking: This will be an open-label study as masking is not feasible given we are comparing twice-a-day to once-a-day regimen and its effect on adherence.
5. Selection and enrollment of subjects
 1. Inclusion criteria
 1. Male or female adult (≥ 18 years old) with a history of solitary kidney transplant within 3 months (± 2 months) of transplant.
 2. Patients must be capable of understanding the purposes and risks of the study and have the ability to give written informed consent and be willing to participate and comply with the study.
 3. Women of childbearing potential and sexually active males must be willing to use contraception, as indicated in Section 6 of the protocol. Subjects who are not of reproductive potential (status post bilateral tubal ligation, bilateral oophorectomy, hysterectomy, or vasectomy), not sexually active, whose current partner(s) is not of reproductive potential, or whose sexual activity is exclusively homosexual are eligible without requiring the use of contraception.
 2. Exclusion criteria
 1. Patients will be excluded if they are pregnant or nursing females or males with a pregnant female partner
 2. Recipient of multiple organ transplant
 3. Recipient of a non-renal organ
 4. Proteinuria > 800 mg/24 hour
 5. eGFR < 30 ml/min
 6. WBC $\leq 2k/mm^3$

7. $\text{Plt} \leq 50\text{k}/\text{mm}^3$
 8. Triglycerides $> 500 \text{ mg/dL}$
 9. HIV positive (HIV ab +)
 10. Unable to tolerate oral medications
 11. Use of another investigational product within thirty days prior to receiving study medication

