 1. For the first three months (± 2 months) post-transplant, the pool of patients from which subject of this study will be recruited will receive the current standard of care. Standard of care is described as a regimen of tacrolimus IR BID (5-12ng/mL) + MMF 1g BID + prednisone QD Three months (± 2 months) post-transplant and at the time of recruitment, they are randomized to one of the two arms to either receive a complete once-a-day regimen or to receive twice-daily regimen.
 2. Post-randomization, subjects will be converted to one of the two arms, as shown below, and followed for a total period of six months (primary endpoint), or until a terminal end point is reached.
 1. Arm 1: Control-- twice-daily regimen of Envarsus QD (5 - 12ng/mL) + MMF (goal dose 1g BID) + prednisone QD for 6 months

2. Arm 2: Intervention-- once-a-day regimen of Envarsus QD (2- 5ng/mL) + everolimus QD (3-8ng/mL) + prednisone QD for 6 months
 1. Envarsus will be supplied for both Arms from Veloxis Pharmaceuticals
2. Adherence assessment
 1. Adherence to the study intervention will be assessed at all study visits noted on the Schedule of Evaluations (Section 5.1), using the eight point Morisky Medication Adherence Scale (MMAS-8) (17).
5. Clinical and laboratory evaluations
 1. Schedule of evaluations

Data Collection Schedule

Report Form		Baseline	Days Post-Conversion							
			7±2	14±3	30±5	60±7	90±7	120±7	150±7	180±7
Informed Consent Obtained		X								
Randomization		X								
Review of Inclusion and Exclusion Criteria		X								
Medical History		X								
Kidney Transplant Recipient		X								
Vital Signs		X					X			X
Review of Medications and Dosing		X								
Clinical assessment*	Adverse events, dosage and adherence, rejection, infection, hospitalization				X	X	X	X	X	X
	MMAS-8, MMSE Scale, and SF36 (15,16,20)	X								X
Laboratory Assessments	CBC and Chem-7 ¹	X*	O	O	O	O	O	O	O	X*
	Everolimus CO ₂		X*	X*	X*	X*	X	X*	X*	X*
	Tacrolimus CO ₂	X*	X*	X*	X*	X*	X	X*	X*	X*
End of Study										X

X=required; O=optional: data will be collected if performed as standard of care; *=not current standard of care

Footnotes:

1. Includes sodium, potassium, chloride, CO₂, BUN, SrCr, glucose, calcium, WBC, HgB, Hct, platelets
2. Tacrolimus and Everolimus concentrations will be 12- or 24-hour levels , drawn in the morning of each assessment

2. Timing of evaluation
 1. Pre-Randomization Evaluations
Baseline

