- 1.** No formal power analysis conducted since this is a pilot study. However, the sample size proposed (n=40) would be able to observe a mean difference between groups in the change of MMAS-8 scores of 2 ± 2 points (95% CI 0.73,3.27) with 87% power. Additionally, a mean difference between groups in the change in the Memphis Side Effect Scale (MSES) of 5 ± 5 points (95% CI 1.83,8.17) would have 87% power in the current sample size. Given the average MSES score of 25 points in kidney transplant patients within 2 years of transplant, this appears to be a feasible outcome (11). In order to demonstrate noninferiority in treatment failure, it would require 400 subjects (200 in each group) to have 80% power, estimating a treatment failure rate of 20% and an acceptable difference of 10%. We expect that 70% of those approached meeting study inclusion/exclusion criteria will agree to participate and that 85% of those that consent and are enrolled in the study will complete all visits. If the 95% CIs for the actual enrollment and completion proportions are outside of these thresholds, then feasibility will not be met. If the 95% CIs encompass these expected values, then feasibility will be met.

3. Missing data and imputation methods

- 1.** Under the intention-to-treat principle, all subjects are included in the analysis. Extensive efforts will be made to keep all missing data to a minimum and minimize loss to follow-up (LTFU). However, it is likely that some missing data may occur.

11. Human subjects

1. Institutional review board (IRB) review and informed consent

- 1.** This protocol, the ICF, and any subsequent modifications must be reviewed and approved by the IRB. A signed and dated ICF must be obtained from the subject as defined in 21CFR50.3. The ICF must also be signed and dated by a member of the study staff qualified to be delegated the authority to obtain informed consent. A copy of the ICF must be given to the subject and the consent process must be documented in the subject's medical record. The PI or delegated sub-Investigator is responsible for ensuring that informed consent is obtained from each patient prior to conducting any study-related activities.

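### The feasibility rule in Section 10.2 has no direction, so 39 or 40 of 40 subjects completing all visits would be scored as not met

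*Combined protocol and SAP*

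**What the plan says.** The whole rule stands in Section 10.2, after the power statement.

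- Expected consent: "We expect that 70% of those approached meeting study inclusion/exclusion criteria will agree to participate".
- Expected completion: "85% of those that consent and are enrolled in the study will complete all visits".
- Not met: "If the 95% CIs for the actual enrollment and completion proportions are outside of these thresholds, then feasibility will not be met".
- Met: "If the 95% CIs encompass these expected values, then feasibility will be met".

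Section 3 (Study design) fixes the denominator for completion: "There will be 20 subjects in each arm, with a total study size of 40 subjects". Neither sentence of the rule says below, above or at least. No interval method is named, and nothing covers the case where one interval contains its value and the other does not. No other section returns to the rule.

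**The concern.** A feasibility criterion should fail when recruitment or retention is too low. This one tests whether the data are compatible with 70% and 85% in either direction. An interval wholly above the expected value does not contain it and lies outside it, so both sentences give the same label: not met. A pilot that retained everyone would have to report that feasibility failed, or reinterpret its own rule after seeing the data.

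The stakes are limited to that label. Feasibility is not among the objectives in Section 1 or the outcomes in Section 10.1, and the stopping examples in Section 11.2 do not use it. The MMAS-8 comparison does not depend on it.

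**Working it through.** **Inputs.** n = 40 (Section 3); expected completion 0.85 and expected consent 0.70 (Section 10.2); 95% two-sided intervals (Section 10.2). The interval method is not stated, so several were tried.

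**The section's own figure.** The feasibility rule states no computed number. The nearby power claim (difference 2, SD 2, 20 per arm) reproduces. A two-sample t-test at two-sided 0.05 (assumed) has noncentrality 2/(2·√(2/20)) = 3.16 on 38 degrees of freedom and power 86.9%, against the stated 87%.

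**Step 1: which completion counts are met?** For each x, check whether the interval for x/40 contains 0.85. Three examples of the arithmetic:

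- Exact, 40/40: lower limit = 0.025^(1/40) = 0.912.
- Wilson, 39/40: (0.975 + 0.0480 − 1.96·√(0.000609 + 0.000600)) / 1.0960 = 0.871.
- Wald, 38/40: 0.95 − 1.96·√(0.95·0.05/40) = 0.882.

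| Completers | Exact 95% CI | Wilson 95% CI | Wald 95% CI | Label as written |
|---|---|---|---|---|
| 29 (72.5%) | 56.1–85.4 | 57.2–83.9 | 58.7–86.3 | met by exact and Wald, not by Wilson |
| 30 (75%) | 58.8–87.3 | 59.8–85.8 | 61.6–88.4 | met |
| 38 (95%) | 83.1–99.4 | 83.5–98.6 | 88.2–100 | met by exact and Wilson, not by Wald |
| 39 (97.5%) | 86.8–99.9 | 87.1–99.6 | 92.7–100 | not met |
| 40 (100%) | 91.2–100 | 91.2–100 | 100–100 | not met |

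Four further methods were checked at 39/40. Their lower limits are 86.0 (Agresti–Coull), 88.9 (Jeffreys), 85.3 (Wilson with continuity correction) and 86.7 (inverted exact binomial test). All exceed 85. At 40/40 the lowest limit from any method is 89.1. The full met range is 29–38 (exact), 29–37 (Wald) and 30–38 (the other five).

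**Step 2: how often would completion fail for being too good?** For exact or Wilson this is P(X ≥ 39) = p^40 + 40(1 − p)p^39. For Wald it is P(X ≥ 38).

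| True completion | Exact or Wilson | Wald |
|---|---|---|
| 85% (planned) | 0.012 | 0.049 |
| 90% | 0.080 | 0.223 |
| 95% | 0.399 | 0.677 |

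At a true rate of 80% the exact or Wilson figure is 0.0015.

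**Step 3: consent (illustrative).** The plan does not give the number to be approached. Assume enrolment stops at 40 and that consenters equal the 40 enrolled. Then 40 of 47 approached is 85.1%, exact interval 71.7–93.8%, wholly above 70% and so not met. The interval lies wholly above 70% when the number approached is at most 47 (exact), 48 (Wilson) or 49 (Wald). The negative binomial chance of this is 0.014, 0.027 and 0.048 if true consent is 70%, and 0.251, 0.358 and 0.472 if it is 80%.

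**Step 4: either criterion.** Assuming independence, the exact-interval chance that at least one fails for being too good is 1 − (1 − 0.014)(1 − 0.012) = 0.026 at 70%/85%, and 1 − (1 − 0.251)(1 − 0.080) = 0.311 at 80%/90%.

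**The case against.** The strongest reply is that the section calls 70% and 85% thresholds, and a threshold for consent or retention is naturally a minimum; no team would call full retention infeasible. That may well be the intent. But the next sentence makes containment the condition for met and calls the same figures expected values, and nothing elsewhere corrects this. Nor does reading them as minimums settle the rule, because it leaves open which limit must clear the value. If the lower limit had to reach 85%, exact and Wilson intervals would pass only 39 and 40 of 40, exactly the results that the literal rule fails.

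The second reply is that it seldom matters. At the planned completion rate this is right: 1.2% by exact or Wilson. The larger probabilities need true rates above plan, which the documents do not support. Completion means attending all visits, and Section 9 allows discontinuation for adverse events or on request, so true completion could equally be lower. The highest figures come from Wald, a poor choice near 100%. This keeps the point minor.

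The consent figures are also open to challenge. Besides the unknown number approached, the enrolment procedures place consent before eligibility is confirmed, so consenters may exceed 40. Those figures show that the same defect exists, not how often it would occur.

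**Conclusion.** The concern holds. Taken as written, the rule labels 39 or 40 completers of 40 as not met and 30 of 40 as met, whichever of seven interval methods is used. At 38 of 40 the unnamed method decides the label. The completion result needs only the planned n of 40 and the stated 85%. The exact-interval result does not hinge on exactly 40: for any enrolment from 36 to 45, completion by all subjects or all but one is likewise not met.

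The severity is minor. The risk is small at the planned rates and becomes material only if the pilot does better than planned. The probabilities for better-than-planned rates and for consent rest on the assumptions stated with them.

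**What to change.** In Section 10.2, state that feasibility is not met only if the upper 95% limit for consent is below 70% or the upper 95% limit for completion is below 85%, and is otherwise met, including when an interval lies wholly above its value. Name the method, for example exact or Wilson. The word 'or' means that one shortfall is enough to fail; this is a choice, and the plan should make it openly.

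The change removes only the too-good failures. The chance that completion is met moves as follows:

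| True completion | Exact, now → revised | Wilson, now → revised |
|---|---|---|
| 85% | 0.976 → 0.988 | 0.958 → 0.970 |
| 90% | 0.919 → 1.000 | 0.918 → 0.999 |
| 95% | 0.601 → 1.000 | 0.601 → 1.000 |

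The chance of not met because completion is low does not change: at a true 75% it is 0.285 (exact) or 0.416 (Wilson) before and after.

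Report the observed proportions and intervals beside the label. At n = 40, completion of 29/40 (exact, Wald) or 30/40 (Wilson) still passes. That reflects limited precision at this size, not an error in the rule. A minimum point estimate or a lower-limit criterion would be stricter alternatives if the investigators want one.

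The cost is one or two sentences. No new data, visits or subjects are needed.

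### Feasibility is declared met whenever the 95% CI fails to exclude the expected value, so at 40 subjects a true completion of 75% against an expected 85% passes 58% to 72% of the time, depending on the unstated interval method

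*Combined protocol and SAP*

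**What the plan says.** The feasibility rule stands at the end of the sample-size paragraph, Section 10.2 of the protocol. Two expectations come first: "We expect that 70% of those approached meeting study inclusion/exclusion criteria will agree to participate", and "85% of those that consent and are enrolled in the study will complete all visits". Two decision sentences follow: "If the 95% CIs for the actual enrollment and completion proportions are outside of these thresholds, then feasibility will not be met", and "If the 95% CIs encompass these expected values, then feasibility will be met".

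The planned size is in Section 3, Study design: "There will be 20 subjects in each arm, with a total study size of 40 subjects". The documents do not name a method for the confidence intervals, a minimum acceptable proportion, a requirement on the lower bound, or the probability that the rule reaches either verdict.

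**The concern.** An interval that contains 85% shows only that the data are compatible with 85%. At 40 subjects the same interval is usually compatible with much lower values too. The rule turns this lack of contradiction into a positive finding, and it has no third outcome for data that cannot settle the question.

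If the rule is followed exactly, the report could state that feasibility was met when completion was about 10 points below the plan's own expectation, and a reader would have no way of telling this from the verdict. It is the only feasibility rule in the plan, so no other criterion would catch the error.

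**Working it through.** **Inputs.** n = 40, 20 per arm (Section 3). Expected completion 85% and enrolment 70% (Section 10.2). 95% intervals, taken as two-sided. Not in the documents, and therefore assumptions: the interval method (five common ones are compared), the true rates used as scenarios, and, for enrolment, that eligible patients are approached until 40 enrol.

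**The plan's own figure.** The plan gives no operating characteristic for the feasibility rule. The nearest check on n = 40 is its statement of a "mean difference between groups in the change of MMAS-8 scores of 2 ± 2 points (95% CI 0.73,3.27) with 87% power". A two-sided two-sample t-test at 5% with 20 per arm, difference 2 and SD 2, has power 86.9%, which reproduces the 87%.

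**Step 1: which completion results pass.** For each x from 0 to 40, compute the 95% CI for x/40 and mark it met if the CI contains 0.85.

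| Method | 95% CI for 29/40 | Results that pass |
|---|---|---|
| Exact (Clopper-Pearson) | 56.1% to 85.4% | 29 to 38 |
| Wald | 58.7% to 86.3% | 29 to 37 |
| Wilson | 57.2% to 83.9% | 30 to 38 |
| Agresti-Coull | 57.0% to 84.0% | 30 to 38 |
| Jeffreys | 57.5% to 84.4% | 30 to 38 |

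The lowest pass is therefore 72.5% or 75%, depending on the method. With the exact interval, 28/40 has an upper bound of 83.4% and fails.

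**Step 2: how often the rule passes.** P(met | p) is the sum over passing x of C(40, x) p^x (1 − p)^(40 − x).

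| True completion | Exact | Wald | Wilson, Agresti-Coull, Jeffreys |
|---|---|---|---|
| 70% | 0.441 | 0.441 | 0.309 |
| 75% | 0.715 | 0.714 | 0.584 |
| 80% | 0.911 | 0.905 | 0.838 |
| 85% | 0.976 | 0.939 | 0.958 |

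The upper end of the passing range hardly matters here: if 39 and 40 completers also passed, the exact value at 75% would be 0.7151 instead of 0.7150.

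**Step 3: enrolment.** If N patients are approached to obtain 40, N follows a negative binomial distribution. With exact intervals the CI for 40/N contains 0.70 for N = 48 to 68. The weakest pass is 40/68 = 58.8% (CI 46.2% to 70.6%). P(met) is 0.629 at a true 60%, 0.881 at 65% and 0.968 at 70%.

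**Step 4: both criteria together.** With true completion 75%, true enrolment 70%, independence and exact intervals: 0.715 × 0.968 = 0.69.

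**Step 5: the three-zone rule, exact intervals.** Completion is met if x ≥ 34 (34/40 = 85%), not met if x ≤ 28, and inconclusive for 29 to 33.

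- P(x ≥ 34) is 0.024 at a true 70%, 0.096 at 75%, 0.286 at 80%, 0.607 at 85% and 0.900 at 90%.
- At a true 75%, the remainder is 0.715 − 0.096 = 0.619 inconclusive and 0.285 not met.
- Enrolment is met if N ≤ 57 (40/57 = 70.2%; 40/58 = 69.0%). P(met) is 0.554 at a true 70%.
- Both met, with the true rates at 85% and 70%: 0.607 × 0.554 = 0.34.
- At least one not met in that case: P(x ≤ 28) = 0.012 and P(N ≥ 69) = 0.018, so 1 − 0.988 × 0.982 = 0.030.

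**The case against.** The best defence is that the plan mostly speaks of expected values. Checking whether data are compatible with an expectation is a weak criterion, but it is less plainly an error than failing to prove a required minimum. Part of this stands: Section 10.2 also calls the figures thresholds, but nowhere describes 85% or 70% as a minimum. The criticism is therefore that the word *met* claims more than the rule can show, and not that a stated requirement is missed.

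Four stronger readings are tempting and are not supported:

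- *That this is the only rule by which the pilot reaches a conclusion.* Section 10.1 defines a primary outcome, the between-arm difference in MMAS-8 change, and Section 11.2 gives numerical examples for stopping after 20 subjects. It is the only feasibility rule, and feasibility is not among the objectives in Section 1 or the outcomes in Section 10.1.
- *That the verdict will be used to justify a larger study.* The same paragraph says that noninferiority would need 400 subjects, but nothing links that number to the feasibility result.
- *That 72.5% passes and that 72% is the error rate.* Both depend on the interval method. With three of the five methods 29/40 fails and the rate is 58%. Both also concern completion alone.
- *That a smaller sample would pass more easily.* This is true of the rule in general, but the plan fixes the size at 40.

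A fair objection to the remedy is that it has no lower-bound requirement either and that it is strict when both criteria are considered together. Both are correct and are stated under the fix.

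**Conclusion.** The point holds. The rule treats failure to exclude the expected value as evidence that it was reached. At 40 subjects, a true completion 10 points below expectation is called met more often than not under all five interval methods: 58% to 72% on completion alone, and about 69% with exact intervals if enrolment must also pass. The joint figure assumes true enrolment of 70%, independence, and approaching patients until 40 enrol. The true completion of 75% is a scenario and not a forecast.

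The consequence is limited to the feasibility statement. Treatment, the MMAS-8 comparison and the safety review are unaffected. It should still be corrected, because following the text exactly gives an unsound conclusion.

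**What to change.** Replace the two decision sentences in Section 10.2 with a three-zone rule that names the exact (Clopper-Pearson) 95% interval and applies to each criterion separately:

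- *Met*: the observed proportion is at least the expected value (completion 34/40 or more; enrolment at least 70%).
- *Not met*: the upper 95% bound is below the expected value (completion 28/40 or fewer).
- *Inconclusive*: anything else (completion 29 to 33 of 40). This is not to be presented as feasible.

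Report both proportions with their 95% CIs whatever the verdict. The counts assume 40 enrolled. The rule also means that 39 or 40 completers out of 40, whose exact intervals lie wholly above 85%, can no longer be read as failing.

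**Cost.** Wording only, with no extra subjects or data. The plan should state the price:

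- At a true 85% completion, the chance of met falls from 0.98 to 0.61.
- At a true 70% enrolment, it falls from 0.97 to about 0.55.
- Both are met together only about 34% of the time when both true rates equal the expectations (independence, approach until 40 enrol). Nearly all the rest is inconclusive; at least one criterion is not met about 3% of the time.

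The plan should also say that met on the point estimate does not prove a true rate of 85%: 34/40 has an exact lower bound of 70.2%.

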Appendix A: Scientific Registry of Transplant Recipients (15)
Program Summary: MUSC

Medical University of South Carolina
Center Code: SCMU
Transplant Program (Organ): Kidney
Release Date: June 16, 2016
Based on Data Available: April 30, 2016

SRTR Program-Specific Report
Feedback?: [contact]
[name]
http://www.srtr.org

A. Program Summary

Figure A1. Waiting list and transplant activity

[figure not shown]
[figure not shown]

Table A1. Census of transplant recipients

Recipients	01/01/2014-12/31/2014	01/01/2015-12/31/2015
Transplanted at this center	187	207
Followed by this center*	1,372	1,134
...transplanted at this program	1,345	1,111
...transplanted elsewhere	27	23

[figure not shown]
* Recipients followed are transplant recipients for whom the center has submitted a post-transplant follow-up form for a transplant that took place before the 12-month interval for each column.

Figure A2. Transplant rates 01/01/2015 - 12/31/2015

(1) Statistically higher (p<0.01)
(2) Statistically higher (p<0.01)

Figure A3. Waiting list mortality rates 01/01/2015 - 12/31/2015

(1) Not significantly different (p=0.087)

Figure A4. First-year adult graft and patient survival: 01/01/2013 - 06/30/2015

[figure not shown]
[figure not shown]

Figure A5. First-year pediatric graft and patient survival: 01/01/2013 - 06/30/2015

